- 2.** Human immunodeficiency virus (HIV) is a key challenge for global health. Vitamin D deficiency is common in people living with HIV infection. Antiretroviral therapy (ART) may create unique risk factors for vitamin D insufficiency, including alterations of vitamin D metabolism by ART. Vitamin D supplementation in HIV-infected patients have not previously been investigated in Pakistan and it is unknown whether sufficient physiological levels is associated with improved clinical outcome or not. This statistical analysis plan (SAP) will give more detailed descriptions of the endpoints in the study and the corresponding analyses.

- 3. Study design:** We have designed this study with the hypothesis, that the addition of high dose of vitamin D supplementation would be effective in elevating serum 25-hydroxy vitamin D concentration into normal physiological range in patients with HIV infection and this would improve their clinical outcome over the period of 6 months' treatment. The primary outcome of the study will be the sufficient elevating level of serum 25-hydroxyvitamin D at 24weeks. Secondary outcome of the study will be, the increase means CD4 count, decrease in viral load and improvement in liver function test and to reduce the severity of clinical symptoms. This is a double-blind randomized placebo-controlled trial. 114, patients aged (19-50) years with diagnosed HIV disease will be recruited by purposive sampling technique from VCCT treatment centre of Government Said Mitha Teaching Hospital located in the walled city of Lahore, Pakistan. The patients will be divided into two arms. Arm-A patients will receive recommended ARV + Vitamin D supplements and patients in Arm-B will receive recommended ARV and placebo. Participants will be randomly allocated to receive 25 hydroxy vitamin D supplementation (n=) or placebo (n=) with the start of ART

	Screening	Treatments			
	V 1 Screening & Assessment	V 2 Randomization & 1 st Dose	V 3 2 nd dose	V 4 3 rd dose	V 5 Post Assessments
	-7~1	1 Day	5 week	12 week	24 week
ICF	×				
Eligibility Criteria	×	×			
Baseline Questionnaire	×				
Weight	×		×	×	×
Height	×		×	×	×
Vital Signs	×	×	×	×	×
Vit-D	×			×	
CD4 count	×			×	
Viral load	×			×	
PCR	×			×	
CBC	×			×	
Study Medication		×	×	×	
AE Monitoring		×	×	×	×
RDA					×
End of Study					×

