6.1 Populations

Intention-to-treat (ITT)

All randomised study subjects. This will be seen as the primary population for the analysis.

Per Protocol (PP)

All randomised study subjects completing the whole study period (complete cases). For a specific analysis, study subjects with missing data on any of the variables in the model will be excluded from the analysis. Analyses of this population is seen as a sensitivity analysis to investigate whether conclusions are sensitive to assumptions regarding the pattern of missing data.

6.2 Groups:

Patients with with vitamin-D deficiency are divided into two groups i.e placebo group and vitamin-D group.

Placebo group: out of total 95 participants 47 participants were on placebo arm

Vitamin-D group:

Similar out of total 95 participants 48 participants were on vitamin-D arm

Vitamin-D deficiency:

All randomized study subjects will be divided into two subgroups according to having vitamin-D deficiency at baseline visit.

Division of groups:

All randomised study subjects will be divided into two subgroups according to treatment.

7. Analyses

All outcomes will be presented using descriptive statistics. As the sample size is low so we will check the normality of each variable on screening (Visit 1) and according to the normality check we will determine the mean difference change in Placebo and active treatment arm.

In descriptive analysis we will mention the mean value of each variable with lower and upper bound with 95% confidence interval, 5% trimmed mean, median, Std. Deviation as per the each group ; normally distributed data by the Mean, Variance, Standard deviation (SD), lower and upper values of the variables to see the outliers if any.

In analytical analysis we will apply T-Test for two independent samples to see the difference between two arms. In case any variable doesn't follow the normality assumptions, we will use non-parametric test.

For the safety objective we will use only frequency/number of events to present it.

SPSS 21 will be used for all statistical analysis.

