7.1 Primary outcome

The primary outcome analysis will be performed to check the difference change in Placebo group and Active Treatment group (Vitamin-D Group) through comparing mean difference from Visit 1 to Visit 4. This test will identify the mean increase or decrease in the Vitamin-D levels in the study Participants.

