7.2 Secondary Outcomes

The secondary outcome analysis will be performed to check the difference change in Placebo group and Active Treatment group (Vitamin-D Group) through comparing mean difference from Visit 1 to Visit 4. This test will identify the mean increase or decrease in the respective variables including CD4 count, PCR detection, Viral Load and Liver Enzymes change.

For the safety objective we will use only frequency/number of events to present it.

For the Socio-Demographic factors association or correlation chi square test or bivariate correlation will be checked with one constant variable (Low Vitamin-D Level on Visit 1).

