7.3 Tertiary Outcomes

In all tertiary objectives, we will check the mean change in the blood counts from Visit 1 to Visit 4 with 95% Confidence Interval by using two independent samples T-Statistics or Non-Parametric test Mann-Whitney U.

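### The SAP and the protocol prescribe different primary analyses of 25(OH)D, at different times, and nothing in the available text says which one governs

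*SAP*

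**What the plan says.** **SAP.** Section 7 says "we will check the normality of each variable on screening (Visit 1) and according to the normality check we will determine the mean difference". It continues: "we will apply T-Test for two independent samples to see the difference between two arms". Where a variable does not "follow the normality assumptions, we will use non-parametric test". Section 7.1 applies this to the primary outcome as a between-arm comparison of the change from Visit 1 to Visit 4, without a covariate, and adds: "This test will identify the mean increase or decrease in the Vitamin-D levels in the study Participants". A specific rank test appears only for the tertiary outcomes, in section 7.3: "two independent samples T-Statistics or Non-Parametric test Mann-Whitney U".

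**Protocol.** Section 7 uses the word primary for one method only: linear regression with adjustment for baseline, with 24 weeks as the example time. The same section says, twice, that a Wilcoxon test compares the two treatments. Section 4.4 adds that effectiveness on 25-hydroxy levels will be evaluated by logistic regression. It gives no cut-off.

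**Precedence.** SAP section 2 says that the SAP "will give more detailed descriptions of the endpoints in the study and the corresponding analyses". It does not say that the SAP replaces the protocol. The part of the SAP before section 2 was not available for this review.

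**The concern.** An analyst holding both documents cannot tell which result is the primary one. One path compares raw change at Visit 4 by a test chosen from the data. The other compares baseline-adjusted levels at 24 weeks. They differ in method, covariate and time.

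Within the SAP path, normality is to be checked on the Visit 1 value, although the variable tested is the change. No normality test or threshold is given, and no statement whether arms are pooled. If the rank branch is taken, the test no longer addresses the mean increase or decrease that section 7.1 promises.

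At stake are the freedom to report whichever analysis is more favourable, and a 24-week conclusion drawn from week-12 samples.

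**Working it through.** **1. The time of the primary measurement, side by side**

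| Place | Time given |
|---|---|
| SAP section 3, text | 24 weeks |
| Protocol section 7 | 24 weeks; a garbled sentence also mentions 3 months |
| Schedule tables (SAP section 3, protocol section 6) | Vitamin D at Visit 1 and Visit 4 only; Visit 4 is week 12 (the protocol table adds a one-day offset) |
| SAP section 7.1 | Visit 1 to Visit 4 |
| Protocol section 5 | 0 and 60 days |
| Protocol section 6.1 visit list | Visit 4 is Day 7 |

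Neither table has a vitamin D sample at week 24.

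**2. The plan's own size.** SAP section 3.1: 60% against 85%, 80% power, 5% level (two-sided assumed).

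n per arm = (1.960 + 0.842)² × (0.60×0.40 + 0.85×0.15) / 0.25² = 7.85 × 0.3675 / 0.0625 ≈ 46.2, so 47 per arm and 94 in total. This reproduces the plan. The figure is for a proportion, so it does not size either continuous analysis. If the dichotomised variable is roughly normal (an assumption), the same contrast is z(0.85) − z(0.60) = 1.036 − 0.253 = 0.783 SD.

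**3. Precision by formula.** Let k be follow-up SD divided by baseline SD, and ρ the correlation. The variance of the change comparison relative to the adjusted one is (1 + k² − 2ρk) / (k²(1 − ρ²)).

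| | ρ = 0.3 | ρ = 0.5 | ρ = 0.7 |
|---|---|---|---|
| k = 1 | 1.54 | 1.33 | 1.18 |
| k = 2 | 1.04 | 1.00 | 1.08 |

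Where the adjusted analysis has 80% power with 47 per arm, the change t-test has 62%, 68% and 73% at k = 1, and 78%, 80% and 77% at k = 2.

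**4. Simulation.** All inputs are assumed: 47 per arm; ρ from 0.3 to 0.7; normal or lognormal data (log SD up to 0.8); k = 1 or 2; shift of 0, 0.5 or about 0.78 follow-up SD. The SAP rule is taken as a pooled Shapiro-Wilk test at 5% on Visit 1, then a t-test or Mann-Whitney on the change. The regression uses robust standard errors.

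- *Type I error (k = 1):* SAP rule followed mechanically 4.4–5.4%; regression 3.8–5.5%.
- *Type I error, better of those two reported:* about 6–8%.
- *t-test, rank test and regression not all agreeing on significance:* about 6–37% at 0.5 SD; 0–15% at about 0.78 SD.
- *Normality verdict on Visit 1 differing from that on the change (0.5 SD shift):* about 9% of trials with normal data, 58–61% with log SD 0.4, 5–6% with log SD 0.8.

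Power at a 0.5 SD shift, SAP rule against raw-scale regression:

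| Data | ρ = 0.3 | ρ = 0.5 | ρ = 0.7 |
|---|---|---|---|
| Normal, k = 1 | 52 vs 70% | 68 vs 79% | 87 vs 91% |
| Log SD 0.8, k = 1 | 82 vs 70% | 92 vs 77% | 99 vs 87% |
| Log SD 0.8, k = 2 | 96 vs 72% | – | – |

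Adjustment therefore gains up to about 18–20 points near normality with equal SDs. It gains little when k = 2. On the raw scale it can lose about 15–24 points under strong skew (92 − 77 = 15; 96 − 72 = 24).

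**The case against.** The strongest reply is that the SAP, as the more detailed document, governs, and that it can be read as one procedure. The natural partner of a two-sample t-test is Mann-Whitney, which section 7.3 pairs with it, and the protocol's Wilcoxon test for two groups is plausibly the same test. The section 7 sentence on variables that fail normality is not itself limited to Visit 1. Neither the Wilcoxon nor the logistic sentence says primary, and the latter sits under data collection. The Day 7 entry belongs to a separate six-visit, 28-day list.

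Much of this stands. It reduces the conflict to two serious candidates, the SAP's test on change and the protocol's adjusted regression, and to one main timing conflict, week 12 against week 24. It does not remove either. No available text gives the SAP precedence, and SAP section 3 itself puts the primary outcome at 24 weeks while section 7.1 analyses Visit 4.

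Three stronger readings are tempting and are not supported:

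- *The normality gate inflates type I error.* Followed mechanically it stays near 5%. The risk lies in choosing between the documents. Treating the t-test and rank test as freely selectable as well gives 7.4–9.5%, but the SAP chooses between those two by rule.
- *The choice of test would probably decide this trial.* Disagreement is common at 0.5 SD. At about 0.78 SD, roughly the planned effect, it is 0–15%.
- *Baseline adjustment is always more powerful.* It is not under strong skew on the raw scale. Eligibility is restricted on baseline vitamin D, so a larger follow-up SD, where the gain is small, is plausible.

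**Conclusion.** The point holds as a contradiction. The two documents define different primary analyses at different times, and a 24-week conclusion would rest on samples that both tables place at week 12. This follows from the text and needs no assumption, subject to the unavailable opening of the SAP.

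The numerical consequence is moderate and conditional: type I error of about 6–8% if the better analysis is reported, and test disagreement that depends strongly on the true effect. These figures rest on assumed correlation, SD ratio, distribution and normality test. Loss of precision is not the reason to act, because its direction depends on the shape of the data.

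SAP section 6.2 already reports 47 and 48 participants by arm in the past tense. A reader might infer that the analysis was chosen after unblinding. Counts by arm do not show that, but they make the date of any change important.

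Missing outcome values, the scale for viral load, PCR detection and a responder analysis are separate questions.

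**What to change.** In both documents:

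1. Name one primary analysis, the protocol's own: linear regression of 25(OH)D on arm and Visit 1 25(OH)D, reported with a 95% CI. State in advance whether 25(OH)D is analysed raw or log-transformed.
2. Delete the Visit 1 normality gate and, for this comparison, the Wilcoxon and logistic sentences. Keep Mann-Whitney on the change as a labelled sensitivity analysis.
3. State which document governs.
4. Reconcile the sampling times in protocol sections 5, 6, 6.1 and 7 and SAP sections 3 and 7.1 to one time. Unless a week-24 vitamin D sample exists, state the conclusion for Visit 4 (week 12).
5. Date the change and say whether it preceded unblinding.

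The cost is wording. The Visit 1 value is already collected, and a Visit 4 conclusion needs no new sample if one Visit 4 sampling time was in fact used. The downside is some loss of power against a rank test if 25(OH)D is strongly skewed and analysed raw. The sensitivity analysis would show this but would not restore the power of the primary test, which is why the scale should be settled in advance.

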7.1 Primary outcome

The primary outcome analysis will be performed to check the difference change in Placebo group and Active Treatment group (Vitamin-D Group) through comparing mean difference from Visit 1 to Visit 4. This test will identify the mean increase or decrease in the Vitamin-D levels in the study Participants.

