Protocol Title

High-Dose Vitamin D3 in the Treatment of Human Immune Deficiency Virus Patients, A Double-Blind Randomized Control Trial

Protocol Version: 1.0

Date: August 15, 2019

Institute of Social & Cultural Studies
University of the Punjab,
Lahore

Abstract

Human immunodeficiency virus is a key challenge for global health. Vitamin D deficiency is common in people living with HIV infection. Antiretroviral therapy may create unique risk factors for vitamin D insufficiency, including alterations of vitamin D metabolism by ART.

The objective of the study is, to know the effect of high dose Vitamin D, in the treatment of HIV patients with antiretroviral therapy. It will be a randomized controlled trial, in which 104 patients visiting Said Mitha Teaching Hospital Lahore will be included.

The patients will be divided into two groups. Group-A patients will receive ARV + Vitamin D supplements and patients in Group-B will receive only antiretroviral therapy and placebo.

Methods/design: A randomized placebo double blind control trials of patients with age 19-50 years will be the participants of our study at VCCT center of said Mitha Teaching Hospital, located in walled city of Lahore, Pakistan. Participants will be randomly allocated to receive 25 hydroxyvitamin D supplementation (n=) or placebo (n=) with the start of ART.

The primary outcome will be achieved with high dose of serum 25-hydroxyvitamin D level at 24 weeks. Secondary outcome will include decrease in viral load, increase mean CD4 count to reduce prevalence of clinical symptoms (elevated levels of LFTs, decrease HB level & serum calcium level). Purposive sampling will be carried out.

Data will be collected through Performa, which will be entered and statistically analyzed, using SPSS version 24.0, This Performa is designed by the Punjab AIDS Control Programme including socio-demographic information, Pretest

information, posttest information & follow up chart. Chi-square test will be used to estimate the association among qualitative variables.

Discussion: High dose Vitamin D supplementation in HIV-infected patients has not previously been investigated in Pakistan and it is unknown whether increasing levels is associated with improved clinical outcome or not. Therefore, it is significant to conduct a study to know the effect of vitamin D in the treatment of HIV patients with antiretroviral therapy.

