4. STUDY PROCEDURES

4.1 Study Population

Patients visiting Said Mitha Teaching Hospital Lahore will be the study population and having diagnosed with HIV positive patients.

4.2 Sampling technique:

Random list was generated for the double blind purpose. This list was generated through Excel sheet.

4.3 Ethical Consideration:

The study will be conducted after approval from the Punjab University Ethical Review Board. Permission will also be obtained from Punjab AIDS Control Programme to use health facilities and this study will be registered at Clinical Trial.gov, to use the health facilities and services of paramedics staff for data collection. Written consent of parents and guardians will be taken before starting the study.

4.4 Data Collection:

All staff involved in the study will be trained by the principal investigator before start of data collection. Trained laboratory technician will screen the patients aged 19 years to 50 years of age in (VDT) diagnostic center of hospital visiting outpatients department in their community and will refer the positive patients to treatment center of AIDS Control Programme clinic of Mayo Hospital Lahore, After receiving their prescribed ART, the two positive groups would be divided into two equal groups, one group will receive 25hydroxy vitamin –D and other halves will receive placebo at the same time once weekly for 12 weeks. Patients will be called for follow-up after every

4 weeks. At the end, we will perform posttest and check the level of 25 hydroxy in both groups and other parameters and by using logistic regression we will evaluate the results of effectiveness of 25 hydroxyin blood levels of HIV patients

4.5 Randomization:

The random allocation sequence will be generated in an excel spread sheet by a statistician who will be independent of the study. Consecutive numbers will be assigned to active vs. placebo in equal numbers. No restrictions (e.g. stratification, block size) will be applied. This sequence will be used by the study pharmacy to label pairs of syringes containing active and placebo medication with a study number assigned to active and placebo arms, respectively. These staff will assign the consecutive ID numbers to participants according to the sequence in which they are enrolled, and the hospital pharmacy then supply syringes of placebo active medication bearing this ID number.

4.6 Blinding:

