Patients of all study participants will be blinded to allocation, as will be the doctors and the staff nurse who will enrol participants and perform study assessments. Active and placebo medication will be presented identically in 1 ml syringes, and will have identical appearance and texture.

4.7 Interventions:

All participants will be treated with vitamin D supplements (Annexure attached) provided by AIDS Control Programme at outpatients department according to WHO guidelines. Vitamin D and calcium will be supplied to HIV positive patients according to the study (Annexure attached) on a weekly basis by suitably trained staff

who will provide information regarding benefits of vitaminD advise as to how it should be taken. Participants who will be randomised to the intervention arm of the trial will receive one oral dose of 100,000 IU (10 mg) vitamin D3 (cholecalciferol) in 1 ml olive oil, will administer via a syringe at 5 and 12 weeks' post-initiation of vitamin D3 supplementation. Participants who will randomised to the control arm of the trial will receive one oral dose of placebo (1 ml extra virgin) via a syringe at 5 and 12 week's post-initiation of vitamin D3 supplementation. After screening further dose of RDA Vitamin-D will be provided for next 5 weeks to complete 24 weeks of study.

5. LAB ANALYSIS AND COLLECTION OF BLOOD SAMPLE:

25-hydroxyvitamin D concentration will be measured 0 and 60 days to assess baseline deficiency and then effect of supplementation, 3ml blood sample will be taken in gel tube after clot formation will be centrifuged. Serum or plasma may be stored for up to 3 days at 2-8 centigrade. Initially **Alere** HIV combo strips will be used for screening of HIV and syphilis, then on positive result we will use second screening on uni-gold HIV strip. Then on third step we will use SD HIV 1/2 3.0 strip for final confirmation of screening step and finally we perform RT-PCR at last.

The haemoglobin level will be determined at 0 days and 60 days to assess the anaemia and effect of supplementation in all selected participants. Blood sample will be drawn from patients who will give their consent voluntarily.

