7. STATISTICAL CONSIDERATION

Statistical analyses will be conducted using SPSS VERSION 23. Qualitative data will be presented in form of frequency and percentage and quantitative data will be presented in form of mean \pm S.D. For the comparison of both treatments (randomly allocated to patients) Wilcoxon test will be applied to compare effectiveness of both treatment plans. P-value ≤ 0.05 will be considered as significant, Baseline characteristics of trial participants will be summarised separately for both randomised group. For each group dichotomous and categorical data of participants will be presented as number and percentages.

The primary outcome, effect of allocation on continuous outcomes that will be assessed both at baseline and at the end of study (e.g. Vitamin-D supplementation at 24 weeks) will be assessed using linear regression, adjusting for the baseline values. The effect of allocation of categorical outcomes variables that will be assessed both at baseline and at the end of study (clinical outcome) will be analysed with generalized linear regression with a log link and binomial distribution to yield a risk ratio adjusted for the baseline

values with 95% CI and p value(**cummings**,2009).. Serum concentration of 25{OH} D will be measured at baseline,05 03 months at baseline, Statistical significance will be inferred where $p < 0.05$.

Allocated to patients) Wilcoxon test will be applied to compare effectiveness of both treatment plans. P-value ≤ 0.05 will be considered as significant.

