3.1 Sample size calculation

Assuming that 60% of patients in the control arm would attain > 30% of their baseline vitamin-D status at 6 months, we calculated that a total of 94 participants (47 per arm) would need to complete follow-up in order to detect a 25% absolute increase (to 85%) in the proportion of patients attaining > 30% vitamin-D level at 6 months in the intervention arm with 80% power at the 5% significance level. (Lake, Vitamin D in HIV-Infected Patients on HAART, 2014).

This number was inflated to a total of 114 to allow for attrition due to death and loss to follow-up. No interim analysis was performed. (Shriver, 2019)

4. Aims and objectives:

Primary objectives

1. To determine whether proposed oral high dose vitamin D3 is sufficient for achieving the physiological concentration in HIV positive patients on ART. (primary outcome)

Secondary objectives

1. To determine whether this intervention also improves CD4 count, viral load count, liver enzyme in study participants. (Efficacy outcome).
2. To discover whether this interventional regimen is safe and well tolerated by study participants. (Safety outcome).
3. To ascertain socio-demographics factors responsible for decreased level of vitamin D3 in HIV positive patients on ART.

Tertiary objectives:

1. To conclude the effects of total leucocytes count in HIV patients with vitamin D supplementation.
2. To determine the effects of total neutrophil count in HIV patients with vitamin-D supplementation.
3. To determine the effects of total eosinophil count in HIV patients with vitamin-D supplementation.
4. To conclude the effects of total monocyte count in HIV patients with vitamin-D supplementation.
5. To establish the effects of total platelets count in HIV patients with vitamin-D supplementation
6. To find out the effects of total hemoglobin count in HIV patients with vitamin-D supplementation
7. To determine the effects of total lymphocytes count in HIV patients with vitamin-D supplementation
8. To see if the effects of total HCT count in HIV patients with vitamin-D supplementation

5. Outcomes

This section will present the outcomes investigated to answer the study aims and objectives. The analyses are described in section 6 Analyses.

5.1 Primary outcome:

1. To determine whether proposed oral high dose vitamin D3 is sufficient for achieving the physiological concentration in HIV positive patients on ART. (primary outcome)

5.2 Secondary outcomes:

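### The primary outcome is declared at 24 weeks, but SAP 7.1 analyses the change to Visit 4, which both schedule tables put at week 12

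*SAP*

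**What the plan says.** **Declared time.** The protocol abstract states: "The primary outcome will be achieved with high dose of serum 25-hydroxyvitamin D level at 24 weeks". SAP 3 agrees: "The primary outcome of the study will be the sufficient elevating level of serum 25-hydroxyvitamin D at 24weeks". Protocol 7 describes the primary regression for outcomes "assessed both at baseline and at the end of study (e.g. Vitamin-D supplementation at 24 weeks". SAP 3.1 bases the sample size on a difference "in the proportion of patients attaining > 30% vitamin-D level at 6 months".

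**Analysed time.** SAP 7.1 compares placebo and vitamin D "through comparing mean difference from Visit 1 to Visit 4". The laboratory change analyses in SAP 7.2 and 7.3 use the same two visits.

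**Schedule.** The tables in Protocol 6 and SAP 3 both head V4 as week 12 (third dose) and V5 as week 24 (post-assessments). Both mark the five laboratory rows at V1 and V4 and leave V5 blank. The protocol table adds that each V4 sample is taken one day after V4; the SAP table does not.

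**Other sampling times.** Protocol 5 states: "25-hydroxyvitamin D concentration will be measured 0 and 60 days". Protocol 7 says that serum 25(OH)D "will be measured at baseline,05 03 months at baseline", which cannot be read with certainty. Protocol 4.4, after describing weekly dosing for 12 weeks, adds: "At the end, we will perform posttest and check the level of 25 hydroxy in both groups and other parameters". Protocol 8.1 speaks of a study of three months. Protocol 6.1 gives a separate list of six visits, with Visit 4 at Day 7 and the last visit at Day 28.

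**The concern.** The time of measurement is part of what a primary outcome is. A trial that declares 25(OH)D at 24 weeks and analyses it at week 12 answers a different question from the one it set. By the schedule tables, the week-12 value is taken at, or one day after, the visit of the third dose, whereas week 24 falls 12 weeks after that visit. Nothing in the documents says that one can stand in for the other. If the output of SAP 7.1 were reported as the 24-week result, the report would misstate what was measured. If the schedule tables were also followed literally, there would be no week-24 value with which to correct it.

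**Working it through.** This is mainly a comparison of passages. The arithmetic is short.

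**1. The plan's own sample size.** Inputs from SAP 3.1: 60% in control, 85% in intervention, both at six months; 80% power; 5% significance, taken here as two-sided because the SAP does not say. With the unpooled normal approximation:

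n per arm = (1.960 + 0.842)² × [0.60 × 0.40 + 0.85 × 0.15] / 0.25² = 7.85 × 0.3675 / 0.0625 = 46.2, rounded up to 47, or 94 in total.

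This reproduces the stated 94 (47 per arm). The figure is sound on its own terms, but its inputs are six-month proportions. The documents give no week-12 rates, so power at week 12 cannot be computed from them.

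**2. Count of laboratory marks, same in both tables** (rows: vitamin D, CD4, viral load, PCR, CBC):

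- V1 (screening): 5 of 5
- V4 (week 12): 5 of 5
- V5 (week 24): 0 of 5

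V5 does carry marks for weight, height, vital signs, adverse events, RDA and end of study, so the column as a whole is not missing. The two tables agree with each other, and SAP 7.1 to 7.3 name Visit 4 independently of them. That makes a fault in reading the PDF an unlikely explanation.

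**3. Distance between the times.**

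- Declared: week 24 = 24 × 7 = day 168.
- Analysed: week 12 = 12 × 7 = day 84 (day 85 with the protocol table's extra day).
- Gap: 168 − 84 = 84 days = 12 weeks.
- Protocol 5's later sample: day 60 = 60 / 7 = week 8.6, which is (168 − 60) / 7 = 15.4 weeks before week 24.

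**4. Does another passage resolve it?** Protocol 7 presupposes a 24-week value. Protocol 5 points to about week 9. The garbled sampling sentence in Protocol 7, the post-test in Protocol 4.4 and the three-month study in Protocol 8.1 lean towards about 12 weeks. None of them redefines Visit 4 as week 24, and the visit list in Protocol 6.1 ends at Day 28.

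**The case against.** The strongest reply is that this is a clerical slip. V5 is headed as the post-assessment visit, Protocol 7 expects a value at 24 weeks, and Protocol 4.4 promises a test at the end, so a V5 sample may have been intended and only its mark omitted. That is possible, and it stands. A reader might infer from the blank cells that no week-24 25(OH)D was planned or taken; the documents do not establish that. But restoring the mark would not cure the conflict, because SAP 7.1 would still stop at Visit 4.

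The opposite reply is that about 12 weeks was intended throughout, as Protocol 4.4 and 8.1 suggest. If so, the declared outcome, the hypothesis and the sample-size time are what must change.

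Three stronger readings should also be set aside.

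- *Visit 4 means Day 7.* Protocol 6.1 says so, but the SAP's own table defines its Visit 4 as week 12. The visit list must be reconciled; it does not show that the primary analysis is planned for Day 7.
- *The trial is underpowered at week 12.* With no week-12 rates, this can be neither shown nor excluded.
- *The visit was chosen after seeing data.* SAP 6.2 already gives 47 placebo and 48 vitamin D participants out of 95, in the past tense. That shows that numbers by arm were known when it was written. It does not show that outcomes were known or that they guided the choice. It is a reason to disclose, not evidence of a data-driven change.

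**Conclusion.** The contradiction is real and must be fixed before the primary result is reported. The declared outcome is at 24 weeks and the sample size rests on six months, while the planned primary analysis ends at week 12, 12 weeks earlier. In both tables, none of the five laboratory rows is marked at week 24.

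The conclusion assumes that the SAP's Visit 4 is the one in its own schedule table. It does not depend on whether a V5 mark was omitted. The documents do not show which time was intended or whether week-24 samples exist, so the remedy has to begin by finding that out.

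**What to change.** **First, establish whether 25(OH)D was, or still can be, measured at V5.** Then:

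1. *Week-24 samples were taken.* Correct both tables, change SAP 7.1 to the change from Visit 1 to Visit 5 (week 24), and keep V4 as a secondary time. Cost: an amendment only.
2. *None taken, and no participant has passed week 24.* Add the V5 draw and make the same changes. Cost: an amendment plus one draw and assay set per participant at a visit that already exists.
3. *Week-24 samples are absent and can no longer be obtained for all participants.* Restate the primary outcome and hypothesis as week 12 and report the result as week 12. Report any week-24 values as secondary, with the number measured in each arm. Date and disclose the change, say whether outcome data or allocation were known when it was made, and state that the six-month sample-size basis was not derived for week 12. Cost: an amendment and a disclosure.

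**In every case:**

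- Define the analysed visit by week in SAP 7.1 to 7.3. Apply the same time to the laboratory change analyses in SAP 7.2 and 7.3, or label them week 12.
- Add a liver-enzyme row at baseline and at the analysed visit, recording whether it was measured. SAP 7.2 analyses liver enzymes, but neither table lists them.
- State whether the V4 sample precedes or follows the V4 dose, and make the two tables agree.
- Reconcile the sampling and visit times in Protocol 4.4, 5, 6.1, 7 and 8.1 with the schedule.
- Reconcile the RDA vitamin D text in Protocol 4.7 with the RDA mark at V5. Neither says which arm receives it, so what a week-24 contrast compares is unsettled. This review does not propose a regimen.
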